3.3.4.2 Discontinuation of the trial by the Sponsor

BI reserves the right to discontinue the trial overall or at a particular trial centre at any time for the following reasons:

1. Failure to meet expected enrolment goals overall or at a particular trial centre
2. Emergence of any efficacy/safety information invalidating the earlier positive benefit-risk-assessment that could significantly affect the continuation of the trial (see also [Section 3.1.1](#)).
3. Violation of GCP, the Clinical Trial Protocol (CTP), or the contract disturbing the appropriate conduct of the trial

The Investigator / the trial centre will be reimbursed for reasonable expenses incurred in case of trial termination (except in case of the third reason).

4 TREATMENTS

4.1 INVESTIGATIONAL TREATMENTS

The trial medication will be provided by BI.

4.1.1 Identity of the investigational Medicinal product and comparator

The characteristics of test products are below:

Substance:	empagliflozin
Pharmaceutical formulation:	film-coated tablet
Source:	Boehringer Ingelheim
Unit strength:	10 mg
Posology:	1 tablet once daily
Rout of administration:	oral

Substance:	placebo matching empagliflozin
Pharmaceutical formulation:	film-coated tablet
Source:	Boehringer Ingelheim
Unit strength:	-
Posology:	1 tablet once daily
Rout of administration:	oral

4.1.2 Selection of doses in the trial

Empagliflozin 10 mg and 25 mg are approved for the treatment of T2DM.

Empagliflozin exerts its effect by promoting glucosuria and consequent hemodynamic changes associated with diuresis, improvement in arterial stiffness, blood pressure lowering effect with no increase in HR and reduction in HR x Pressure product, an index of myocardial oxygen consumption. These modes of actions support the scientific rationale of using empagliflozin in patients with HF.

In the EMPA-REG-OUTCOME trial both doses were administered to patients with T2DM and showed to be equally effective in reducing CV death, HHF, and composite of HHF or CV death in patients with HF at baseline.

In subgroup analysis empagliflozin improved the main outcome of CV death and HHF with the similar magnitude in patients with low or high levels of HbA1c at baseline. This indicates the risk reduction for HF outcome is independent of the degree of glycaemic control at baseline, suggesting that these benefits can be achieved with the 10 mg dose similar to the 25

Proprietary confidential information © 2019 Boehringer Ingelheim International GmbH or one or more of its affiliated companies

mg dose in the non-diabetic population as well. The mechanism of action is supported by studies in healthy volunteers where both doses were associated with about 50g glucosuria.

Given the lower exposure with 10 mg empagliflozin similar general safety, and CV effects similar for both doses, empagliflozin 10 mg once daily has been selected in this trial.

For further details see current version of the IB.

4.1.3 Method of assigning patients to treatment groups

During Visit 2 eligible patients will be randomised to receive empagliflozin 10 mg, or matching placebo, in a 1:1 ratio according to the randomisation plan. The assignment will occur in a blinded fashion via Interactive Response Technology (IRT).

To facilitate the use of the IRT, the Investigator will receive a manual including all necessary instructions for using the system. A copy of the manual will be available in the ISF.

Patient assignment to the treatment group will be determined by a computer generated random sequence. Access to the randomisation code will be controlled and documented - for further details please refer to [Section 4.1.5.1](#). and [4.1.5.2](#).

Using this procedure, relevant parties will be blinded to the treatment group assignment.

For information on stratification and capping please refer to [Section 3.3](#).

4.1.4 Drug assignment and administration of doses for each patient

Patients who qualify will be randomised to one of the dosages described in [Section 4.1.1](#). Trial medication will be dispensed in a double-blind and single-dummy manner.

Dispensing of kits for the double-blind treatment period will begin at Visit 2 and continue at every visit until end of trial. For further details regarding packaging (e.g. number of tablets per container) please refer to [Section 4.1.6](#).

From the start of the treatment period patients will be instructed to take the trial medication once daily with a glass of water. Empagliflozin can be taken with or without food.

To ensure a dose interval of about 24 hours, the medication should be taken in the morning at approximately the same time every day. If a dose is missed by more than 12 hours, that dose should be skipped and the next dose should be taken as scheduled. On days before the next visit, the dose should be taken 22-26 hours before the planned dose at the visit. No double doses should be taken.

Patients should be instructed not to take their medication on the morning of trial visits as they will be dosed whilst in the clinic. Visits should be routinely scheduled at approximately the same time of day for each visit. The actual date and time of administration of the trial medication at the trial visit will be recorded in the eCRF.

4.1.5 Blinding and procedures for unblinding

4.1.5.1 Blinding

Patients, Investigators and everyone involved in trial conduct or analysis or with any other interest in this double-blind trial, will remain blinded with regard to the randomised treatment assignments until after database lock.

The DMC will be provided with unblinded data in order to allow them to review efficacy and safety and to fulfil their tasks as outlined in the data monitoring committee charter. An independent team, not otherwise involved in the conduct of the trial, will provide the unblinded results to the DMC.

The randomisation code will be kept secret by Clinical Trial Support up to database lock.

4.1.5.2 Unblinding and breaking the code

Emergency unblinding will be available to the Investigator via the IRT. It must only be used in an emergency situation when the identity of the trial medication must be known to the Investigator in order to provide appropriate medical treatment or otherwise assure safety of trial participants. Whenever possible and if time allows, the need for unblinding will be discussed with the medical representative from the Sponsor or delegate before the unblinding of trial medication takes place. The reason for unblinding must be documented in the source documents and/or appropriate eCRF page along with the date and the initials of the person who broke the code.

The patient could continue with trial medication after unblinding.

Due to the requirements to report Suspected Unexpected Serious Adverse Reactions (SUSARs), it may be necessary for a representative from BI's Pharmacovigilance group to access the randomisation code for individual patients during trial conduct. The access to the code will only be given to authorised Pharmacovigilance representatives and not to be shared further.

For Japan only: In this blinded trial, an emergency code break will be available to the Investigator / the sub-Investigators via the IRT. This code break may only be accessed in emergency situations when the identity of the trial medication must be known to the Investigator /the sub-Investigators in order to provide appropriate medical treatment or if required to assure the safety of trial participants. Each site receives a manual from the IRT provider that contains instructions on how to unblind the treatment of a patient via the IRT (via 24-hour Emergency helpline). If the code break for a patient is accessed, the Sponsor or delegate must be informed immediately. The reason for accessing the code break, together with the date, must be documented on the appropriate eCRF page. In case third party needs to break the code, however, when the Investigator cannot be reached, the code can be opened by calling emergency code manager.

4.1.6 Packaging, labelling and re-supply

The investigational products will be provided by BI or a designated CRO. They will be packaged and labelled in accordance with the principles of Good Manufacturing Practice

Proprietary confidential information © 2019 Boehringer Ingelheim International GmbH or one or more of its affiliated companies

(GMP). Re-supply to the sites will be managed via the IRT, which will also monitor expiry dates of supplies available at the sites.

For details of packaging and the description of the label, please refer to the ISF.

4.1.7 Storage conditions

Trial medication must be stored under the recommended storage conditions indicated on the label. A temperature log must be maintained by the investigator / pharmacist / investigational drug storage manager to make certain that the drug supplies are stored at the correct temperature. If the storage conditions are found to be outside the specified range, the process outlined in the ISF should be followed.

4.1.8 Drug accountability

The Investigator and/or Pharmacist and/or investigational drug storage manager will receive the investigational drugs delivered by the Sponsor or delegate when the following requirements are fulfilled:

- Approval of the trial protocol by the Institutional Review Board (IRB) / ethics committee
- Availability of a signed and dated clinical trial contract between the Sponsor or delegate and the head of the investigational site,
- Approval/notification of the regulatory authority, e.g. competent authority (CA),
- Availability of the curriculum vitae of the principal Investigator,
- Availability of a signed and dated clinical trial protocol
- Availability of the proof of a medical license for the principal Investigator
- For USA; Availability of Form 1572

The Investigator and/or Pharmacist and/or investigational drug storage manager must maintain records of the product's delivery to the trial site, the inventory at the site, the use by each patient, and the return to the Sponsor, CRO or warehouse / drug distribution centre or alternative disposal of unused products. If applicable, the Sponsor, CRO or warehouse / drug distribution centre will maintain records of the disposal.

These records will include dates, quantities, batch / serial numbers, expiry ('use-by') dates, and the unique code numbers assigned to the investigational product and trial patients. The Investigator / Pharmacist / investigational drug storage manager will maintain records that document adequately that the patients were provided the doses specified by the CTP and reconcile all investigational products received from the Sponsor or delegate. At the time of return to the Sponsor/CRO, the Investigator / Pharmacist / investigational drug storage manager must verify that all unused or partially used drug supplies have been returned by the clinical trial patient and that no remaining supplies are in the Investigator's possession.

4.2 OTHER TREATMENTS, EMERGENCY PROCEDURES, RESTRICTIONS

4.2.1 Other treatments and emergency procedures

The use of medication for the treatment of HF will be at the discretion of the Investigator and should be in accordance with local/international guidelines.

Proprietary confidential information © 2019 Boehringer Ingelheim International GmbH or one or more of its affiliated companies

All concomitant (additional) medications and other therapies should be recorded on the appropriate pages of the eCRF.

Concomitant antidiabetic medications should be adjusted individually as clinically indicated by the patient's usual diabetes care provider. Restrictions of antidiabetic background therapy are described in [Section 4.2.2](#).

Patients without a diagnosis of DM experiencing repeated or severe symptoms such as nervousness, sweating, intense hunger, trembling, weakness and palpitations should contact the Investigator or other healthcare professional, as these symptoms might be suggestive of hypoglycaemia. In the case of hypoglycaemia, in patients with or without DM, that may put the patient at risk (e.g. repeated symptomatic hypoglycaemia or severe hypoglycaemia), appropriate care should be provided at the discretion of the Investigator.

Special attention must be paid to the prevention of KA. All patients must be made aware of this risk and need to be instructed to contact the Investigator or other healthcare professional in case of symptoms of metabolic acidosis, KA and DKA. Cases of DKA have been reported in patients treated with empagliflozin, including fatal cases. In a number of reported cases, the presentation of the condition was atypical with only moderately increased blood glucose values; below 14 mmol/l (250 mg/dl).

The risk of DKA must be considered in the event of non-specific symptoms such as nausea, vomiting, anorexia, abdominal pain, excessive thirst, difficulty breathing, confusion, unusual fatigue or sleepiness.

Patients should be assessed and treated for KA immediately according to local guidelines if these symptoms occur, regardless of blood glucose level. If KA is suspected, the trial medication should be discontinued, the patient should be evaluated, and prompt treatment should be initiated.

Patients who may be at higher risk of KA while taking empagliflozin include patients on a very low carbohydrate diet (as the combination may further increase ketone body production), patients with an acute illness, pancreatic disorders suggesting insulin deficiency (e.g. Type 1 diabetes mellitus (T1DM), history of pancreatitis or pancreatic surgery), insulin dose reduction (including insulin pump failure), alcohol abuse, severe dehydration, and patients with a history of KA. Empagliflozin should be used with caution in these patients. In patients requiring insulin, caution should be taken when the dose of insulin is reduced.

In clinical situations known to predispose to KA (e.g. prolonged fasting due to acute illness or surgery), the Investigator should consider monitoring for KA and temporarily discontinue the trial medication.

There are no trial specific emergency procedures to be followed.

4.2.2 Restrictions

The use of any SGLT-2 inhibitors or combined SGLT-1 and 2 inhibitors except the blinded trial medication is prohibited during the course of the trial. This does not include the 30 days

Proprietary confidential information © 2019 Boehringer Ingelheim International GmbH or one or more of its affiliated companies

period between the EOT and the Follow Up Visit occurring at study close-out (see [section 6.2.3](#)).

If any restricted treatment is given during the conduct of the trial, the trial medication can be discontinued temporarily, or if needed permanently.

If the patient is in need of any additional treatment during this period, this may be given at the discretion of the Investigator. The patient can still remain on trial medication.

WOCBP must use the contraception methods as described in the patient information.

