Adverse events	X	X	X	X	X	X	X	X	X	X	X	X	X	X	X	X	X	X	5.3.7
KCCQ		X		X		X		X									X	X	5.2.1
EQ-5D		X		X		X		X				X				X	X	X	5.6.1
HCRU		X	X	X		X		X		X		X		X		X	X		5.6.2
Urine Pregnancy Test ¹³	X	X	X	X		X		X		X		X		X		X	X		5.3.4.2
Safety lab Tests	X ¹⁴	X	X	X		X		X		X		X		X		X	X	X	5.3.4
NT-proBNP	X	X	X	X				X				X					X	X	5.5
High-sensitivity TroponinT		X																	5.5
HbA1c ¹⁵	X	X		X		X		X		X		X		X		X	X		-

Trial Period	Screening ¹	Randomised Treatment Period ²															Follow Up Period ³		Relevant CTP section
		2	3	4	5 Phone call	6	7 Phone call	8	9 Phone call	10	11 Phone call	12	13 Phone call	14	15 Phone call	16	EOT Visit	FU Visit ³	
Visit	1																		
Trial week	-3	1	4	12	22	32	42	52	64	76	88	100	112	124	136	148	EOT Visit	EOT + 30 days	
Days from Randomisation Visit window ⁴	-28 to - 4	1	29±7	85 ±7	155 ±7	225 ±7	295 ±7	365 ±7	449 ±7	533 ±7	617 ±7	701 ±7	785 ±7	869 ±7	953 ±7	1037 ±7	---	---	
Fasting status ⁵	NF	F	NF	NF	-	NF		NF	-	NF	-	NF	-	NF	-	NF	F	F	
Lipid profile panel		X						X				X					X	X	5.3.4
eGFR (CKD-EPI _{cr} formula)	X	X	X	X		X		X		X		X		X		X	X	X	5.3.4.1
UACR	X	X	X	X		X		X		X		X		X		X	X	X	5.3.4
PK sampling (substudy) ¹⁶				X															5.4.1
Sampling for biobanking of serum/plasma/urine/ DNA (optional, requires separate informed consent) ¹⁷		X ¹⁸		X				X											5.5.1
Dispense trial medication ¹⁹		X	X	X		X		X		X		X		X		X			4.1.4 6.2.2
Return Medication/ medication compliance check			X	X		X		X		X		X		X		X	X		4.3

1. The screening procedures can be done on different days within the time window.
2. From Visit 8 and onwards, on-site visits will be scheduled every 24 weeks until end of trial.
Patients who prematurely discontinue trial medication will perform EOT visit and Follow Up visit, and then continue with scheduled visits until the trial is stopped.
For patients not willing to attend scheduled visits, telephone calls must be made regularly (ref. [Section 3.3.4.1](#)) to document any occurrence of outcome events and vital status.
If the trial continues beyond 148 weeks, visits are to be repeated with same intervals as from week 64 and onwards.
3. Timepoint for the EOT will be communicated via an Investigator letter when the Sponsor is confident that required number of events will be reached within a reasonable timeframe (ref. [Section 3.1](#) and [6.2.3](#)). All patients will have a follow up visit 30 days following regular or premature completion of the treatment period.

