In clinical studies, empagliflozin was well tolerated in both healthy volunteers and patients with T2DM including patients with high CV risk up to a median duration of 2.6 years. The frequency of overall Adverse Events (AEs), AEs leading to discontinuation and Serious AE (SAEs) were comparable to placebo. There was no significant increase in frequency of hypoglycaemia with empagliflozin compared to placebo except when used in combination with a sulphonylurea or basal insulin. In general there was a small increase in frequency of urinary tract infection (UTI) compared to placebo. There was an increase in frequency of genital infections with the use of empagliflozin. There was a small increase in total cholesterol, low-density lipoprotein (LDL) cholesterol and high-density lipoprotein (HDL) cholesterol and no significant changes in triglycerides. No changes in electrolytes were observed with empagliflozin.

In the EMPA-REG OUTCOME trial renal function over time, as measured by the eGFR, is shown in [Figure 1.2.3:1 \[P16-06807\]](#). After the initial decrease, eGFR remained steady in the empagliflozin group and was reversed after the cessation of the trial medication ([Figure 1.2.3:2](#)). At the follow-up visit, the adjusted mean difference from placebo in the change from baseline in the eGFR with each of the two doses of empagliflozin was 4.7 ml per minute per 1.73 m² (95% confidence interval, 4.0 to 5.5; $P < 0.001$ for both comparisons) ([Figure 1.2.3:2](#)). The data indicated that the initial drop in eGFR after administration of empagliflozin is reversible and most likely due to hemodynamic changes. This is very similar to what have been observed with ACEi and ARBs. The EMPA-REG OUTCOME trial also generated the hypothesis that the expected deterioration in renal function in patients with T2DM slowed

Proprietary confidential information © 2019 Boehringer Ingelheim International GmbH or one or more of its affiliated companies

down after using empagliflozin, and this will be further tested in the HF trials using the eGFR slope analysis and composite renal endpoints (see [Section 5.1.2](#) and [5.1.3](#)).

Proprietary confidential information © 2019 Boehringer Ingelheim International GmbH or one or more of its affiliated companies

[figure not shown]

Figure 1.2.3:1 Change in eGFR over 192 weeks in the EMPA-REG OUTCOME trial.

[figure not shown]

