5.1.3 Further endpoints

- Time from first to second adjudicated HHF

Proprietary confidential information © 2019 Boehringer Ingelheim International GmbH or one or more of its affiliated companies

- Time to first all-cause hospitalisation
- Occurrence of adjudicated HHF within 30 days after first adjudicated HHF
- Occurrence of adjudicated HHF and CV death. This endpoint will account for clinical hierarchies in composite outcomes, i.e. CV death is ascribed greater importance than HHF (see win ratio in [Section 7.3.3](#))
- New onset of atrial fibrillation
- Adjudicated MI (fatal or non-fatal)
- Adjudicated stroke (fatal or non-fatal)
- Adjudicated TIA
- Composite of time to first event of all-cause mortality and all cause hospitalisation
- Composite of adjudicated CV death or adjudicated non-fatal MI
- Composite of adjudicated CV death or adjudicated non-fatal stroke
- Adjudicated CV death, adjudicated non-fatal MI, adjudicated non-fatal stroke (3-point MACE)
- Progression to macro albuminuria (defined as UACR >300 mg/g) from baseline for patients with baseline UACR ≤ 300 mg/g
- Time to first new onset of sustained normo- or micro albuminuria (UACR ≤ 300 mg/g) in patients with macro albuminuria at baseline
- Time to first new onset of sustained normo albuminuria (UACR < 30 mg/g) in patients with micro- or macro albuminuria at baseline
- eGFR (CKD-EPI)_{cr} change from baseline to 30 days after treatment stop
- Composite of sustained reduction of ≥40% eGFR (CKD-EPI)_{cr} or sustained eGFR (CKD-EPI)_{cr} <15 mL/min/1.73 m² (< 10 mL/min/1.73 m² for patients with eGFR (CKD-EPI)_{cr} < 30mL/min/1.73 m² at baseline), or adjudicated CV death
- Composite of sustained reduction of ≥40% eGFR (CKD-EPI)_{cr} or sustained eGFR (CKD-EPI)_{cr} <15 mL/min/1.73 m² (< 10 mL/min/1.73 m² for patients with eGFR (CKD-EPI)_{cr} < 30mL/min/1.73 m² at baseline), or all-cause mortality
- Composite of sustained reduction of ≥40% eGFR (CKD-EPI)_{cr} or sustained eGFR (CKD-EPI)_{cr} <15 mL/min/1.73 m² (< 10 mL/min/1.73 m² for patients with eGFR (CKD-EPI)_{cr} < 30mL/min/1.73 m² at baseline), adjudicated CV death, or adjudicated HHF

Proprietary confidential information © 2019 Boehringer Ingelheim International GmbH or one or more of its affiliated companies

- Change from baseline in KCCQ overall summary score at week 52
- Change from baseline in KCCQ total symptom score at week 52
- Change from baseline in KCCQ individual domains at week 52

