7.3.3 Further endpoint analyses

Further time-to-event endpoints will be analysed in the same Cox proportional hazards model as the primary analysis.

Change from baseline to 30 days after treatment stop of eGFR (CKD-EPI)_{cr} will be evaluated by an ANCOVA model, including treatment group, gender, geographical region and history of DM as fixed effect and baseline eGFR (CKD-EPI)_{cr} (continuous), age (continuous), LVEF (continuous) as linear covariates.

An unmatched win ratio considering adjudicated CV death and adjudicated HHF will be analysed based on unmatched pairs. All patients randomised to empagliflozin will be compared to all patients randomised to placebo. Only common follow-up time will be considered for the comparison. Patients on empagliflozin are considered to have “won” the comparison if either the other patient has died while the patient on empagliflozin was still alive, or if both patients did not die, then if the other patient had more occurrences of HHF, or if the number of occurrences of HHF is the same but the time to the first occurrence of HHF is longer. The number of comparisons won is noted as N_W . Patients on empagliflozin are considered to have “lost” the comparison if the empagliflozin patient died while the patient on placebo was still alive, or if both patients did not die, then if the patient on empagliflozin had more occurrences of HHF, or if the number of occurrences of HHF is the same but the time to the first occurrence of HHF is shorter. The number of comparisons lost is noted as N_L . The win ratio is N_W / N_L .

The rules for winning and losing follow a modified Rogers 2014 [[R16-4909](#)] approach also considering the time to the first HHF event in case of a tie on the number of HHF events. The analysis of the unmatched win ratio will be conducted as described in Pocock 2012 [[R16-4813](#)].

Further longitudinal continuous endpoints will be analysed in a MMRM, including age, LVEF and eGFR (CKD-EPI)_{cr} at baseline as linear covariates and visit by treatment

Proprietary confidential information © 2019 Boehringer Ingelheim International GmbH or one or more of its affiliated companies

interaction, baseline by visit interaction, geographical region, gender and baseline history of DM as fixed effects.

The details of analyses will be defined in the TSAP prior to unblinding.

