7.5 HANDLING OF MISSING DATA

There will be no imputation of data for safety data or for time-to event endpoints. For patients who discontinue the trial treatment prematurely, all efforts will be made to follow patients for survival and for any other endpoints including the primary and key secondary endpoints until the end of the trial.

For the slope analysis of eGFR (CKD-EPI)_{cr}, all available on-treatment change from baseline data will be used. Patients without on-treatment data after randomisation will not be included in this analysis.

For the analysis of change from baseline to 30 days after treatment stop, only available data will be used. Only patients with post-treatment data will be used in this analysis.

For other longitudinal endpoints such as KCCQ scores, MMRM methodology will be used. Models will be run on both all observed data and all observed on-treatment data. Details of the imputation rule will be given in the statistical analysis plan.

Proprietary confidential information © 2019 Boehringer Ingelheim International GmbH or one or more of its affiliated companies

An eGFR (CDK-EPI)_{cr} reduction is considered sustained, if it is determined by two or more consecutive post-baseline central laboratory measurements separated by at least 30 days (first to last of the consecutive eGFR values). If there is no additional measurement after the eGFR reduction is observed and the patient dies within 60 days of this measurement without second measurement ≥ 30 days after the first, then the eGFR reduction is also considered sustained.

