Rationale for change	To clarify that the collection of the MRS assessment for a stroke that occurs within the last 90 days before the end of the trial will be done at the final study visit for that individual patient. As severity of non-fatal stroke is not part of the primary, secondary, or other endpoints of this study the last MRS assessment in these patients will be less than 90 days after their stroke in order not to delay the end of the trial.
-----------------------------	---

11.3 GLOBAL AMENDMENT 3

Date of amendment	20 Nov 2019
EudraCT number	2016-002278-11
EU number	
BI Trial number	1245.110
BI Investigational Product(s)	Empagliflozin
Title of protocol	A phase III randomised, double-blind trial to evaluate efficacy and safety of once daily empagliflozin 10 mg compared to placebo, in patients with chronic Heart Failure with preserved Ejection Fraction (HFpEF).
Global Amendment due to urgent safety reasons	
Global Amendment	
Section to be changed	4.2.2 Restrictions
Description of change	
The use of any SGLT-2 inhibitors or combined SGLT-1 and 2 inhibitors except the blinded trial medication is prohibited during the course of the trial. This also includes the 30 days period between the EOT and the Follow Up Visit.
 
Was changed to:
 
The use of any SGLT-2 inhibitors or combined SGLT-1 and 2 inhibitors except the blinded trial medication is prohibited during the course of the trial. This does not include the 30 days period between the EOT and the Follow Up Visit occurring at study close-out (see section 6.2.3).

Rationale for change	The use of SGLT-2 inhibitors or combined SGLT-1 and 2 inhibitors does not need to be prohibited

Proprietary confidential information © 2019 Boehringer Ingelheim International GmbH or one or more of its affiliated companies

	
during the follow-up period as the patient is no longer taking the study medication, and because events which occur during the follow-up period at study close out are not to be included in the primary analysis. Furthermore investigators are encouraged to treat patients to the best standard of care in compliance with local guidelines and recommendations for HF and diabetes if present (see section 2.3).

Section to be changed
	
7.3.1 Primary endpoint analyses

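### SGLT-2 inhibitors are now allowed before the close-out Follow Up Visit, but that visit's eGFR is still analysed as the value 30 days after treatment stop, with no rule for patients who took one

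*Protocol*

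**What the plan says.** Section 4.2.2 of the current Protocol states that use of any SGLT-2 or combined SGLT-1/2 inhibitor "except the blinded trial medication is prohibited during the course of the trial". It then excludes from the ban the 30-day "period between the EOT and the Follow Up Visit occurring at study close-out". This exclusion came with Global Amendment 3 (Section 11.3).

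The Flow Chart (footnote 3) places a visit after every end of treatment: "All patients will have a follow up visit 30 days following regular or premature completion of the treatment period". The Flow Chart marks eGFR at that visit, and Section 6.2.3 lists blood sampling and concomitant therapy among its procedures.

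Section 5.1.3 keeps as a further endpoint "eGFR (CKD-EPI)_{cr} change from baseline to 30 days after treatment stop". Section 7.3.3 gives the method: "Change from baseline to 30 days after treatment stop of eGFR (CKD-EPI)_{cr} will be evaluated by an ANCOVA model". Its terms are treatment group, gender, region, history of DM, baseline eGFR, age and LVEF. Section 7.5 limits the analysis to available data and adds: "Only patients with post-treatment data will be used in this analysis". Neither section mentions SGLT-2 inhibitor use after EOT.

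**The concern.** A value taken 30 days after stopping is informative because the early eGFR fall on this drug class is thought to be haemodynamic and reversible. Section 1.2.3 says of the earlier T2DM outcome trial that "eGFR remained steady in the empagliflozin group and was reversed after the cessation of the trial medication".

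A patient on empagliflozin who moves straight to a prescribed SGLT-2 inhibitor at close-out has not washed out. A placebo patient who starts one may be in a fresh acute dip when sampled. Both values would enter the analysis labelled as post-treatment.

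At stake is the within-arm reading, that is, how far eGFR returns towards baseline once the drug is stopped. The endpoint also becomes a mixture, because patients who stopped early had their 30-day sample while the ban was in force.

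**Working it through.** The Protocol gives no figure for this point to reproduce, so the check is first textual and then illustrative.

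**Textual check**

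1. Rule: SGLT-2 inhibitors are allowed between EOT and the close-out Follow Up Visit (4.2.2). The exemption is confined to close-out; the 30-day visit after premature discontinuation stays under the ban.
2. Source of the value: the Follow Up Visit, after regular or premature end of treatment (Flow Chart, 6.2.3).
3. Analysis: one ANCOVA over both kinds of visit (7.3.3), on available post-treatment data (7.5), with no exclusion, censoring or covariate for SGLT-2 inhibitor use.
4. Amendment 3's reasons (Section 11.3): the patient is no longer on study medication; "events which occur during the follow-up period at study close out are not to be included in the primary analysis"; and investigators are encouraged to treat to best standard of care. None of the three addresses post-treatment eGFR. The same amendment revised primary censoring, the slope model, the MMRMs and the win ratio, but left this ANCOVA and its data rule unchanged.
5. Reach: the primary analysis stops at the end of the planned treatment phase (7.3.1), and the eGFR slope uses on-treatment data (7.3.2, 7.5). Neither uses this sample.

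**Illustration of size**

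Let pE and pP be the shares of the empagliflozin and placebo arms taking an SGLT-2 inhibitor when sampled, and d the acute dip, taken as the same and additive in both arms. These inputs are assumptions, not figures from the Protocol: uptake 10 to 30%, d = 2 to 4 mL/min/1.73 m².

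- Shift of an arm's mean = −p × d. Lowest: 0.10 × 2 = 0.2. Highest: 0.30 × 4 = 1.2.
- Shift of the between-arm difference = −(pE − pP) × d. Equal uptake: 0. A 10-point gap: 0.10 × 2 = 0.2 to 0.10 × 4 = 0.4. A gap of 30% against 10%: 0.20 × 2 = 0.4 to 0.20 × 4 = 0.8.

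For scale, Section 1.2.3 reports an off-drug difference from placebo of 4.7 in the earlier trial. With equal uptake 4.7 stays 4.7. With 30% in the empagliflozin arm and 10% in placebo it would read 4.3 to 3.9; with the shares reversed, 5.1 to 5.5.

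**Is the uptake range plausible?** The enrolment minimums in Section 3.3 (35% DM, 15% pre-DM, 20% non-diabetic) put the diabetic share between 35% and 100 − 15 − 20 = 65%. If only diabetic patients started a drug, 10% overall would mean 0.10/0.65 = 15% to 0.10/0.35 = 29% of them, and 30% overall would mean 0.30/0.65 = 46% to 0.30/0.35 = 86%. The upper end is therefore demanding for a 30-day window.

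**The case against.** The strongest reply is that the planned comparison is between arms. Patients and investigators stay blinded until database lock (4.1.5.1) and randomisation is stratified by diabetes status (7.6), so uptake should be similar and the contrast little affected. This stands. A reader might infer a biased treatment effect, but nothing in the Protocol supports unequal uptake.

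Second, the endpoint's name remains literally true of trial medication, Section 7.5 is mainly a no-imputation rule, and Section 7.3.3 leaves details to the SAP, which is not shown. This has some force: the Protocol does not say that such values must be kept. But Amendment 3 changed the condition under which the value is measured and left its analysis as it was. Followed as written, the Protocol pools two exposure conditions under one label.

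Third, a reader might take the 4.7 in Section 1.2.3 as the size of the acute dip and arrive at a shift of 0.30 × 4.7 = 1.4. The text does not allow this: 4.7 is a between-arm difference at an off-drug follow-up visit. Nor is it right that the amendment considered only primary-endpoint events; it gives three reasons, though none covers this endpoint.

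Fourth, dropping patients who started a drug selects on a prescribing choice made after randomisation, which may itself depend on eGFR or diabetes. That is correct, and it is why a filtered analysis should not stand alone.

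**Conclusion.** The point holds, at modest weight. Section 4.2.2 and the analysis of post-treatment eGFR are not reconciled. Read as an off-drug value, the within-arm change would be too low in both arms, by 0.2 to 1.2 mL/min/1.73 m² under the assumed uptake and dip. The between-arm contrast is sound if uptake is equal and the dip additive, and otherwise moves by 0.2 to 0.4 per 10-point difference in uptake.

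Actual uptake is unknown. Close-out visits probably supply most of the values, since every patient still on treatment reaches one, but that is an inference without a figure behind it.

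This is one exploratory further endpoint outside the testing hierarchy. A reader might suspect that the primary result or the key secondary eGFR slope is contaminated; neither uses data from this window.

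**What to change.** In Sections 7.3.3 and 7.5, or in the SAP with a reference from there, and before unblinding:

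- prespecify an off-drug analysis of eGFR change to 30 days after treatment stop, using only follow-up samples with no SGLT-2 or combined SGLT-1/2 inhibitor taken since the last trial dose;
- report it alongside the analysis of all available values;
- give, by arm, the proportion who started such a drug before the sample.

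Concomitant therapy is already recorded at the Follow Up Visit, so the cost is a dataset flag and a few sentences. The downsides are fewer patients in the off-drug analysis and selection on a post-randomisation prescribing choice; keeping both analyses shows how much that selection matters. No change to the medication rule is proposed. What needs reconciling is 4.2.2 with the endpoint's analysis.
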